6.2.2 INTERVENTION FIDELITY

We will ensure the consistent delivery of study interventions (BRIGHT, AC) via the following mechanisms. First, tele-sessions in both groups will be recorded. The trained PC will review randomly selected sessions (17%) to monitor for therapeutic drift⁸⁵ and assess fidelity quantitatively using a modified version of the BRIGHT Fidelity and Competence Scale.⁸⁶ Second, at the conclusion of each session, the interventionist will complete the electronic case report form (eCRF) for fidelity monitoring which assesses session completion, duration, content delivered, and delivery mode. For AC, fidelity monitoring will also include assessments of negative fidelity to ensure that BID is not discussed. The accuracy of fidelity self-reporting for the video-recorded sessions is enhanced through the bogus pipeline.⁸⁷ Third, the specific duties necessary to ensure consistent and optimal delivery of the interventions (BRIGHT, AC) are detailed in the respective manuals, thereby minimizing therapeutic drift.⁸⁵ If insufficient fidelity to the manual is identified, the interventionist will be remediated until competency is demonstrated.

6.3 MEASURES TO MINIMIZE BIAS: RANDOMIZATION AND BLINDING

Bias will be minimized through the randomized permuted block design. Randomization will occur at the individual patient level. Following provision of written informed consent and completion of baseline study assessments, patients will be randomized 1:1 to BRIGHT or AC using a stratified permuted block

randomization design with randomly selected block sizes of 4 or 6 to avoid deterministic treatment allocation. Randomization will be stratified by site (MUSC, HFH, WUSM) and free flap reconstruction (yes/no) to minimize variability in practices or patient characteristics between sites. The random allocation sequence will be generated by the lead study biostatistician using a computer-generated algorithm. The program coordinator will implement the random allocation sequence using the REDCap randomization feature to conceal the sequence until intervention assignment. Randomization errors will be handled as per ITT analyses for the efficacy population.

Study investigators will be blinded to allocation. Outcome assessors are not blinded to allocation, but all study assessments are patient-reported outcomes and thus unlikely to be biased by outcome assessors knowing study allocation. Staff delivering BRIGHT/AC cannot be blinded due to face-to-face intervention delivery. Patients are not blinded but they also are not instructed whether BRIGHT or AC is the active intervention.

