4 STUDY DESIGN

4.1 OVERALL DESIGN

We will perform a multisite RCT comparing BRIGHT with AC to test our hypothesis that BRIGHT reduces BID among HNC survivors as measured by change from baseline in IMAGE-HN score (primary objective). In this multisite, parallel-group RCT, patients from MUSC, WUSM, and HFH will be allocated to the two study arms (BRIGHT or AC) as follows. Upon enrollment and completion of the baseline assessments, patients will be randomized 1:1 to BRIGHT or AC using a stratified permuted block randomization design with randomly selected block sizes of 4 or 6. Randomization will be stratified by site (MUSC, HFH, WUSM) and free flap reconstruction (yes/no) to minimize variability in practices or patient characteristics between sites. Randomization will occur at the individual patient level.

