If the patient is interested in participating in the research study, the program coordinator will discuss participation in the trial at that clinical encounter. Because IMAGE-HN is not used in clinic as standard of care at each site, a waiver of documentation of the informed consent process will be utilized to allow for IMAGE-HN to be used as a screening tool for the trial. The potential participant will complete the IMAGE-HN to determine trial eligibility; those with an IMAGE-HN score <22 do not have clinically significant HNC-related BID and thus are not eligible. At this in-person clinic visit the program coordinator will confirm the rest of the inclusion/exclusion criteria that could not be obtained in the EHR.

Each site (MUSC, HFH, WUSM) will use a clinic-based screening and recruitment approach that we optimized in our prior studies.^{4,16,27,40} Recruitment for the study will occur using the standard operating procedures (SOPs) that we optimized during our single-arm and pilot RCTs of BRIGHT at MUSC. These SOPs will be adapted and optimized for clinic workflow at HFH and WUSM. The recruitment protocols have been optimized based on our experiences in prior studies to address logistical issues related to coordination of clinic-based screening and enrollment. Our experience recruiting for BRIGHT also demonstrated that the active clinical practice of the site-PI and his clinical relationship with all members of the multidisciplinary HNC team are key factors in maximizing recruitment. Recruitment at each site will be handled by the project coordinator and study team at that site.

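### Printed block sizes of 4 or 6, visible to the coordinator who recruits and randomizes, reduce but do not eliminate deterministic allocation

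*Protocol*

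**What the plan says.** - **Design.** Section 6.3 describes 1:1 allocation by permuted blocks, stratified by three sites and by free flap reconstruction (yes/no), with a "randomization design with randomly selected block sizes of 4 or 6 to avoid deterministic treatment allocation". Section 4.1 repeats the sizes: "randomization design with randomly selected block sizes of 4 or 6".
- **Who allocates.** Section 6.3: "The program coordinator will implement the random allocation sequence using the REDCap randomization feature to conceal the sequence until intervention assignment". The lead study biostatistician generates the sequence.
- **Who recruits.** Section 5.5.3: "Recruitment at each site will be handled by the project coordinator and study team at that site". Sections 5.5.3 and 8.1 also have the program coordinator preview the clinic schedule, obtain the screening IMAGE-HN and confirm the remaining eligibility criteria.
- **Blinding.** Section 6.3 blinds the study investigators. It also states "Outcome assessors are not blinded to allocation", and patients and interventionists are not blinded either. No sentence blinds the coordinator.
- **Access to documents.** Section 9.5.1 lets study personnel outside the lead site download study documents.

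**The concern.** Section 6.3 gives the purpose of the random block sizes as preventing allocations that can be known in advance. That protection is weakened if the people who enrol patients know which sizes are possible. REDCap hides the upcoming sequence but not the assignments already made. Because site is a stratification factor, each site sees the whole history of its own two strata.

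What is at stake is selection at enrolment. Randomization follows consent and baseline assessment, so foreknowledge could act only earlier: on whom to approach, when, and how warmly to encourage. The remark in section 6.3 that self-reported outcomes are unlikely to be biased by unblinded assessors concerns measurement. It does not address this route.

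**Working it through.** The protocol gives no predictability figure, so there is none to reproduce. Its stated power of 83.7% (section 9.2) does reproduce, at 83.67%: noncentral t, design effect 1 + 9 × 0.05 = 1.45, 16 degrees of freedom. This point does not affect it.

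**Inputs**
- Block sizes 4 or 6, ratio 1:1 (sections 4.1, 6.3).
- Strata: 3 sites × 2 free-flap levels = 6 (section 6.3).
- Planned enrolment 226 (section 9.2), so 226 / 6 ≈ 38 per stratum.
- Assumptions not in the protocol: even strata, and each size drawn with probability 0.5.

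**Step 1: certain allocations exist.** A block of 4 holds two of each arm. Three like assignments within the first four places of a block therefore rule out size 4. The block must be 6, and the rest of it is fixed. For the first block of a stratum, where the starting point is known:
- A block of 6 has 20 equally likely orders. In 2 of them the first three assignments are alike, which makes the last 3 certain.
- In 6 more, the third like assignment falls at place four, which makes the last 2 certain.
- Expected certain allocations in the first block = 0.5 × [(2/20) × 3 + (6/20) × 2] = 0.5 × 0.9 = 0.45.

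That such allocations exist does not depend on how often each size is drawn.

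**Step 2: the whole stratum.** After the first block its boundary may be uncertain, so I used a Bayesian filter over every within-block state consistent with the observed history. An allocation counts as certain when all those states give the same next arm. Results from 20,000 to 30,000 simulated strata of 38 patients, for an observer who knows the sizes:

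| Block sizes | Certain | Best guess right | Callable at ≥ 75% |
|---|---|---|---|
| Fixed 4 | 32% | 70% | 32% |
| Fixed 6 | 24% | 68% | 30% |
| Random 4, 6 (protocol) | 5.6–5.7% | 69% | 48% |
| Random 6, 8, 10 | 1.7–1.8% | 66% | 26% |

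For the protocol's scheme, 0.057 × 226 ≈ 13 allocations are certain, and about 60% of strata contain at least one. With strata of 30 the certain share is again 5.7%.

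**Step 3: what disclosure adds.** Take an observer who knows nothing about block sizes and always guesses the arm that is behind, tossing a coin when the arms are level. Under sizes 4 and 6 (40,000 simulated strata):
- level, 39.0% of allocations, right 50%
- one behind, 49.0%, right 78.3%
- two behind, 11.0%, right 91.0%
- three behind, 1.0%, right 100%

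Overall: 0.390 × 0.50 + 0.490 × 0.783 + 0.110 × 0.910 + 0.010 × 1.00 ≈ 0.689. This equals the best-guess rate of the observer who knows the sizes. Knowing the sizes therefore adds certainty for about 13 allocations and leaves the overall hit rate unchanged.

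**The case against.** The strongest reply is that the method is sound. A statistician generates the list, REDCap conceals it, and random sizes already remove roughly four-fifths of the certain allocations that fixed blocks would leave. The treating physician introduces the study, rosters are reviewed systematically, and eligibility turns on a fixed patient-completed score. Exploiting the pattern would require a coordinator to track two strata and then alter the approach or its timing, and nothing in the protocol suggests that anyone would. All of this stands, and it keeps the point modest.

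A reader might also draw three stronger conclusions that the documents do not support:
- **That printing the sizes causes the 69% best-guess rate.** Step 3 shows that it does not. The cause is small blocks with visible past assignments.
- **That the random sizes fail in their purpose.** They fall short of it. Certain allocations drop from 24–32% to about 6%.
- **That any resulting bias is beyond the analysis.** Section 9.4.2 adjusts for baseline IMAGE-HN, site, free flap, gender, education, employment, tumor location and adjuvant therapy. What remains is selection on unmeasured factors, such as motivation.

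The fall from 48% to 26% callable also needs care. The 75% threshold lies just below the 78% reached at an imbalance of one under sizes 4 and 6. The overall hit rate falls only from 69% to 66%.

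That the coordinator is unblinded and knows the sizes is inferred from the assigned tasks and the document sharing. No sentence says so directly.

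**Conclusion.** The point holds as a limited design weakness. Sections 4.1 and 6.3 disclose the sizes, and the role that recruits also allocates and sees past assignments. For an observer who tracks assignments and knows the sizes, about 5.7% of allocations (about 13 of 226) are certain, so the aim stated in section 6.3 is only partly met. The figure rests on even strata and equally likely sizes; the existence of certain allocations rests on neither. It shows an opportunity for selection. It is not evidence that selection would occur, and no effect on power or on the estimated treatment difference follows from it.

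**What to change.** 1. Remove the block sizes from sections 4.1 and 6.3 and from other site-facing documents. Wording such as *randomly varying block sizes, held by the lead study biostatistician* is enough.
2. For any allocation list not yet in use, have the biostatistician choose a wider, undisclosed set of sizes that includes larger blocks. Even if it became known, a set of 6, 8 and 10 would leave about 1.7% of allocations certain and 26% callable at 75% or better, against 5.7% and 48% now.
3. Replacing a list already in use is optional. Deleting the text does not help where staff already know the sizes, but the gain from a mid-trial reload is small enough to leave to the trial team.

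The cost is a short amendment and, where step 2 applies, a new REDCap allocation table. The downside is a slightly larger possible imbalance within a stratum.

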6.4 STUDY INTERVENTION ADHERENCE

Adherence of subjects to BRIGHT/AC study procedures are key to ensure scientific rigor, validity, reproducibility, and achievement of study objectives. Adherence will be assessed with the following measures: (1) attendance at intervention visits; (2) duration of study visits; (3) homework completion (for BRIGHT); (4) interventionist rating of patient engagement and material comprehension. Attendance at all study visits is mandatory to remain an active participant. Adherence information will be assessed by the interventionist and documented in the eCRF after each study visit.

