6.5 CONCOMITANT THERAPY

For this protocol, participants may use antidepressants and anxiolytics at the discretion of their treating providers. Medication usage will be assessed at each study visit and documented in the eCRF.

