7 STUDY INTERVENTION DISCONTINUATION AND PARTICIPANT DISCONTINUATION/WITHDRAWAL

7.1 DISCONTINUATION OF STUDY INTERVENTION/EXPERIMENTAL MANIPULATION

At subject, PI, or study team member request.

When a subject discontinues from BRIGHT or AC but not from the study, remaining study procedures will be completed as indicated by the study protocol. The data to be collected at the time of study intervention discontinuation will include the following:

- The reason(s) for discontinuing the participant from the intervention, and methods for determining the need to discontinue
- If the participant is due to complete assessments within 2 weeks of being discontinued from the study intervention, those assessments will be administered at the time of discontinuation; if the next scheduled assessments are more than 2 weeks from the discontinuation date, the discontinued participant will wait for the next scheduled assessment. Thereafter, the participant will be included in all future scheduled assessments, even though not participating in the intervention.

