7.2 PARTICIPANT DISCONTINUATION/WITHDRAWAL FROM THE STUDY

Participants are free to withdraw from participation in the study at any time upon request. The investigators will seek to minimize participant discontinuation/withdrawal from the study (see **Section 7.3, Lost to Follow-Up**) except for safety reasons.

An investigator or the IRB may discontinue a participant from the study for the following reasons:

- Significant study intervention non-compliance
- Lost-to-follow up; unable to contact subject (see **Section 7.3, Lost to Follow-Up**)
- Any event or medical condition or situation occurs such that continued collection of follow-up study data would not be in the best interest of the participant or might require an additional treatment that would confound the interpretation of the study

The date and reason for participant discontinuation or withdrawal from the study will be recorded in the eCRF.

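### Sections 6.4 and 7.2 allow missed sessions or non-compliance to end collection of the 6-month primary endpoint, which 7.1 and 9.3 rely on

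*Protocol*

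**What the plan says.** Four sections of the protocol bear on a patient who misses sessions or does not comply.

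- **6.4 (Study Intervention Adherence):** "Attendance at all study visits is mandatory to remain an active participant". The section defines neither the status nor the consequence of losing it. Its list of adherence measures names two kinds of visit: "1) attendance at intervention visits; (2) duration of study visits".
- **7.1 (Discontinuation of Study Intervention):** this covers the case "When a subject discontinues from BRIGHT or AC but not from the study". For such a patient, "the participant will be included in all future scheduled assessments, even though not participating in the intervention".
- **7.2 (Discontinuation/Withdrawal from the Study):** the stated aim is retention: "The investigators will seek to minimize participant discontinuation/withdrawal from the study". It then adds "An investigator or the IRB may discontinue a participant from the study for the following reasons", and the first reason listed is "Significant study intervention non-compliance". No threshold is given.
- **7.3 (Lost to Follow-Up):** a missed visit is rescheduled within 2 weeks. A patient counts as lost only after two missed visits and at least 5 failed contact attempts. The site is also asked to establish whether the patient should continue, without a criterion.

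On the analysis side, the 9.3 primary set needs a completed baseline and 6-month IMAGE-HN and groups patients by randomised arm irrespective of what they received. A separate per-protocol set holds those who completed 6 weeks of intervention. Section 9.4.1 says the primary GEE is valid only if data are missing completely at random.

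**The concern.** An as-randomised comparison of the 6-month change is only as good as the follow-up of patients who did not take the full intervention. Sections 7.1 and 9.3 presume that they are measured. The 7.2 non-compliance ground acts on study participation, not only on the intervention, and 6.4 ties a participant status to full attendance. A site could use either to stop outcome collection in a patient whose only departure is poor adherence.

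That patient would drop out of the primary analysis because of a post-randomisation event. The arms differ in content, in delivering staff and in homework (BRIGHT only), so adherence could differ between them, and three sites could apply an undefined term and an unquantified ground differently. A score that was never collected cannot be recovered by any later analysis plan.

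**Working it through.** **1. What does 6.4 cover?** Its heading, and its closing sentence that the interventionist documents adherence after each visit, point to the treatment sessions. Table 1 places the adherence and interventionist self-report rows under the six sessions. Elsewhere the term is wider. In 6.5, "Medication usage will be assessed at each study visit", and Table 1 continues medication assessment into follow-up. Section 7.3 uses the term for a return to clinic, whereas sessions are by video. The session reading is the natural one, but it is not fixed in the text.

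**2. Which rule governs a non-compliant patient?** Section 7.1 gives the default for a patient who is off the intervention and still in the study. Section 7.2 permits removal from the study for intervention non-compliance. Nothing says when such a patient moves from the first to the second.

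**3. What follows if the patient is removed?**
- There is no 6-month IMAGE-HN, so the patient is outside the primary evaluable set.
- Missingness depends on adherence, so it is not completely at random.
- The full analysis set has two sensitivity analyses for a missing 6-month survey: the baseline score carried over (no change) and the maximum score. Each assigns one fixed value, and neither uses what the patient would have reported.

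**4. Power, starting from the plan's own figure.** Inputs from 9.2: difference 9, SD 16, ICC 0.05, 9 clusters per arm, two-sided 0.05. With m patients per cluster,

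SE = sqrt(2 × 16² × (1 + (m − 1) × 0.05) / (9m)), tested by noncentral t with 2 × 9 − 2 = 16 df.

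For m = 10 (N = 180): SE = sqrt(512 × 1.45 / 90) = 2.872 and 9/2.872 = 3.134, giving power 83.7%. This reproduces the stated figure.

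Now assume that a further 5% or 10% of the 226 enrolled are removed for non-adherence. Pilot attrition was 11/54. Section 5.5.5 calls the pilot's recurrence and second-cancer rate (7 of the 11) likely aberrant, so a second scenario halves those losses: 11 − 3.5 = 7.5 of 54.

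| Base attrition | Extra removal | Evaluable | m | SE | Power |
|---|---|---|---|---|---|
| 11/54 | 5% | 226 × (43/54 − 0.05) = 168.7 | 9.37 | 2.935 | 82.1% |
| 11/54 | 10% | 226 × (43/54 − 0.10) = 157.4 | 8.74 | 3.004 | 80.3% |
| 7.5/54 | 5% | 226 × (46.5/54 − 0.05) = 183.3 | 10.18 | 2.855 | 84.1% |
| 7.5/54 | 10% | 226 × (46.5/54 − 0.10) = 172.0 | 9.56 | 2.915 | 82.6% |

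**5. Bias, by assumption only.** If a share p of one arm is removed, that arm's observed mean change shifts by p × (mean of retained − mean of removed). For an assumed gap of 9 points: 0.05 × 9 = 0.45, 0.10 × 9 = 0.9 and 0.20 × 9 = 1.8 points, against the 9-point target. The same removal in both arms would cancel.

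**6. Pilot evidence.** Section 5.5.5 accounts for the 11 patients off study as 7 with recurrence or a second malignancy, 3 withdrawals for intercurrent physical demands and 1 erroneous enrolment. None is reported as removed for missed sessions or non-compliance.

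**The case against.** The strongest reply is that the protocol already has a follow-up rule. Section 7.1 is the default. Section 7.2 is a separate, discretionary tier, limited to significant non-compliance and set under an aim of minimising withdrawal. Section 6.4, read in place, concerns sessions and may mean no more than being active in the intervention. Section 9.3, with its own per-protocol set, shows the intent to measure non-completers. Most of this stands. A reader might infer that the protocol has no rule at all, or that 6.4 flatly contradicts 7.1. The text supports neither.

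A reader might also infer that the missing-data plan has no answer. That goes too far as well. There are two full-analysis-set analyses, one of them assigning the worst possible score. Section 9.4.1 provides a switch to a mixed model if missingness is significant, names no analysis set for that switch, and leaves the detail to an update of the SAP. The evaluable-set restriction in 9.4.2 is written for the secondary models and cannot simply be carried over to the contingent primary one.

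Finally, the harm is hypothetical on the document's own evidence. That limits the size of the point. It does not remove the opening: 7.2 still permits study removal for non-adherence alone, without a threshold, and no choice of model recovers an outcome that was not collected.

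**Conclusion.** The point holds as a conditional one and should be addressed. To the extent that 6.4 or 7.2 is used to end follow-up, the primary endpoint goes missing because of adherence, which conflicts with 9.4.1 and with the as-randomised analysis in 9.3. Nothing shows that this will be common, and a bias in favour of either arm cannot be inferred. Power stays between 80.3% and 84.1% under the assumed further 5% to 10% removal, so power is not the reason to act. The shifts of 0.45 to 1.8 points rest entirely on removal in one arm and an assumed 9-point gap. Confidence is medium, because the benign reading of 6.4 is the more natural one and 7.2 is discretionary.

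**What to change.** Reconcile 6.4 and 7.2 with 7.1, 7.3 and 9.3. In 6.4, define the participant status and the visits it refers to. In 6.4 and 7.2, state that missed sessions or intervention non-compliance are recorded as adherence data and do not by themselves end scheduled IMAGE-HN collection. Leave unchanged withdrawal of consent, the 7.2 ground on the participant's best interest, and all decisions on stopping the intervention. The change concerns outcome collection only.

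The cost is a short amendment and some extra contact effort for patients who do not attend. Section 7.1 already asks for such follow-up in those who stop the intervention but stay in the study.
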